6.1 Visit procedures

Procedure for scheduled visits and telephone contacts are described in the following and in the flow chart (Table 1).

Table 1 Flow chart

Visit number	Visit 1	Visit 2	Visit 3	Visit 4	Visit 5	Visit 6	Visit 7	Visit 8	Visit 9	Visit 10	Visit 11	Visit 12	Follow-up
Time related to time of implantation (weeks)	-0.5	0 ¹⁾	0	1.5	3	4	5	7	11	15	16	17	
Visit window (days)				±2 ²⁾	±5	±5	±5	±5	±5	±5	±5	±7 ⁴⁾	²⁾
Name of visit	Screening	Inclusion	Implantation	Device mounting	Start-up visit	One-week observation	Two weeks observation	Four weeks observation	Eight weeks observation	Device explantation	End of study		
Screening, Informed consent	X												
Safety blood measurements	X												
Concomitant illness/medical history	X												
Demography	X												
Physical examination	X				X						X		
ECG	X												
Concomitant medication	X	X	X	X	X	X	X	X	X	X	X	X	
In/exclusion criteria	X	X											
Withdrawal criteria			X	X	X	X	X	X	X	X	X		
Device implantation			X										
Suture removal				X								X	
Photography of device fitting					X								
EEG quality test					X						X		
CGM mounting					X				X				
Mounting of external device				X									
Collecting data for calibration start				X									
Hypoglycaemia alarm "on"					X	X	X	X	X	X	X		
Adverse events registration			X	X	X	X	X	X	X	X	X	X	
Adverse device effect registration				X	X	X	X	X	X	X	X	X	
Induced hypoglycaemia							X				X		
Log book				X	X	X	X	X	X	X	X		
Questionnaire					X			X		X		X	
Device explantation												X	
Surgeon questionnaire			X									X	
UNEEG™ medical staff present			X ⁷⁾	X ⁷⁾	X ⁷⁾	X ⁷⁾	X ⁷⁾	X ⁷⁾	X ⁷⁾	X ⁷⁾	X ⁷⁾	X ⁷⁾	X

¹⁾ Inclusion should take place as soon as all screening (including laboratory results) are available, reviewed and subject is confirmed eligible and no later than two weeks after screening. This visit can be performed as a telephone consultation after reviewing blood samples

²⁾ Removal of sutures should be within a time window of 8-12 days following implantation and explantation, respectively

⁴⁾ The explantation of the implanted device should take place as soon as possible following the end of study visit

⁷⁾ Optional

6.1.1 Early discontinuation

In case of early discontinuation, either requested by the subject or at the discretion of the investigator, the end-of-study-form must be completed. The subject must be followed up, as appropriate.

6.1.2 Adverse events

6.1.2.1 Definitions

Adverse event

An adverse event (AE) is defined as any untoward medical occurrence in a subject whether related to the device or not.

This includes events from the first study related activity after subject has signed the informed consent and until removal of sutures (visit 12), see flow chart Table 1.

A worsening in concomitant illness must be recorded as an AE. A worsening of an ongoing AE should be recorded on a new AE form by making a new assessment for seriousness and possible relationship to hyposafe H02 device or implantation procedure.

Adverse device effect

An adverse device effect (ADE) is defined as any untoward and unintended response to a medical device including insufficiencies or inadequacies in instructions for use or deployment, the implantation, the operation, or any malfunction of the investigational medical device. This also includes any event that is a result of a use error or intentional misuse of the device.

Serious adverse event

An serious adverse event (SAE) is defined as an AE that results in any of the following:

- Death
- A life-threatening experience⁷
- In-subject hospitalisation or prolongation of existing hospitalisation
- A persistent or significant disability/incapacity
- A congenital anomaly/birth defect

Serious adverse device effect

Serious adverse device effect (SADE) is defined as an ADE that has resulted in any of the consequences characteristics of a SAE or that might have led to any of these consequences if suitable action had not been taken, intervention had not been made or if circumstances had been less fortunate. These are handled under the SAE reporting system.

⁷ The term "life-threatening" refers to an event in which the subject was at risk of death at the time of the event; it does not refer to an event which hypothetically might have caused death if it were more severe

6.1.2.2 Collection, recording and reporting of adverse events

All events meeting the definition of an AE/ADE must be collected and reported. During each contact with the site (site visit or telephone contact) the subject must be asked about AEs/ADE.

The sponsor will discuss with the investigator all SAEs/SADEs and co-ordinate appropriate actions. Investigator will be informed of any study related procedure SAEs/SADEs that may warrant a change in any study procedure. If the sponsor or the safety committee find continuation of the study incompatible with the safety of the study subjects due to any safety issues related to the hyposafe H02 or the study procedures, the study will be terminated or postponed until these issues have been solved.

UNEEG™ medical must report all SAEs/SADEs to the ethics committee and the Danish Health and Medicines Authority according to the national regulations.

6.1.2.3 Follow-up of adverse events

During and following a subject's participation in a clinical study, the investigator should ensure that adequate medical care is provided for any subject for any AE.

6.1.3 Concomitant illness/medical history

A concomitant illness is any illness that is present at the start of the study (visit 1) or found as a result of the screening procedure. Medical history is a medical event that the subject has experienced in the past. Any changes in the concomitant illness should be recorded during the study. A clinically significant worsening of a concomitant illness must be reported as an AE (see section [6.1.2.2](#)).

6.1.4 Concomitant medication

Concomitant medication is any medication, which is taken during the study. Detail on concomitant medication must be recorded at visit 1. Changes in concomitant medication must be recorded at each visit as they occur.

6.1.5 Hypoglycaemia awareness status

The Pedersen-Bjergaard method (24) and recent history of severe hypoglycaemia will be used to assess hypoglycaemia awareness status at visit 1.

For the Pedersen-Bjergaard method, the subject will be asked: "Do you recognise symptoms when you have a hypo?" and can select one of the following answers:

- Always
- Usually
- Occasionally
- Never

Subjects answering "occasionally" or "never" (i.e. unaware according to Pedersen-Bjergaard method) *and/or* who has experienced at least one severe hypoglycaemic episode within the preceding year will be classified as having impaired awareness of hypoglycaemia.

6.2 Case report forms

Case report forms (CRFs) are provided in a uniform design, each form heading requires identification of the hospital, subject and investigator and each visit must be dated. The investigator must ensure that data are recorded in the CRF as soon as possible after the visit. Completed CRFs must be reviewed and signed by the local investigators. The CRF must be kept on site until the designated CRA has performed verification of all data entries.

6.3 Traceability and recording of the investigational device

At the site, a device accountability system will be maintained during the study, documenting device shipment and receipt, storage at the site, use, and return to the sponsor of used/unused devices, as applicable.

6.4 Monitoring

The sponsor will appoint a qualified, experienced and trained Clinical Research Associate (CRA) from the Contract Research Organisation (CRO) who will visit the study centre periodically during the study. The CRA is to ensure adherence to the clinical investigation plan, including verification of subject informed consent, letter of authorisation, inclusion and exclusion criteria etc. The CRA should also verify and review all AEs/ADEs and SAEs/SADEs.

Investigators must provide access to the hospital files and any other medical source document containing subject's clinical/medical information, to the CRA for them to perform source document verification. The CRA is responsible for verifying the data entered into the CRFs against hospital source documents to ensure accuracy and completeness of the data, prior to retrieving the CRFs, from the study centre.

During the study CRA must check that appropriate written informed consents and power of attorney have been obtained. The CRA must inform the sponsor about any problems relating to facilities, technical equipment or medical staff at the study centre. The CRA must notify such deficiencies in writing to the related clinical centre's principal investigator and convene with the study centre personnel appropriate and timely corrective actions. The CRA must make written reports to the sponsor, after each visit or contact with the investigator or centre.

6.5 Data management

Data management is the responsibility of UNEEG™ medical but may be delegated under an agreement of transfer of responsibilities to a CRO. Data collected via the CRFs will be subject to data quality control measures in compliance with all applicable data management procedures. All CRFs will be audited against corresponding database output to ensure accuracy. Data management will correct obvious errors, and a query will be sent to the CRA for confirmation of the correction by the investigator, as will queries for omission and discrepancies or other errors. The CRFs will be corrected as required and the corrected data entered into the database. The copy of the signed query form will be filed with the CRFs.

Prior to database lock the database will be validated. When all queries have been resolved, the database will be locked. Any changes to the database after that time will require joint written agreement between the investigator, the biostatistician and the sponsor.

7 Statistical considerations and data reporting

Tabulations and cross-tabulations will be performed as outlined in the endpoint analysis section. No comparative statistical analyses are planned. Any deviations from the planned statistical analysis will be justified in the study report.

7.1 Rational for the choice of sample size

This is not a comparative endpoint study. It is assumed that sufficient information about the performance, safety and the use of the hyposafe H02 to support any potential optimisation of the algorithm or adjustment of procedures will be obtained with approximately 12 subjects with type 1 diabetes. The total number will depend on the results of the study and number of withdrawals, and it is planned to enrol 12-20 subjects with type 1 diabetes to ensure a number of subjects completing the study of at least 12.

7.2 Definition of analysis populations

The following analysis set are defined according: Full analysis set (FAS) are all subjects included in the study will be included in the FAS. Per protocol (PP) analysis set are all subjects of the FAS who completed the trial without major protocol violations will be included in the PP analysis set. Safety analysis set are all subjects in whom the investigational device was implanted will be included in the safety analysis set

7.3 Demographics and baseline characteristics

Demographic and baseline characteristics will be summarised according to the type of data. Summaries will be provided for entire study population.

7.4 Handling of missing data

Subjects who withdraw from the study due to reasons not related to the hyposafe H02 device will be tabulated with the reasons for the withdrawal.

7.5 Endpoint analysis

7.5.1 Performance endpoints

All performance endpoints will be analysed using the FAS as well as the PP analysis set.

Primary performance endpoint

The primary performance endpoints are defined as the sensitivity and positive predictive value of the hyposafe H02 based on spontaneous hypoglycaemic episodes.

Spontaneous hypoglycaemic episodes are recorded by subjects in the log book throughout the study. This includes information on blood glucose measurements before treating the episode, alarms given by the hyposafe H02 device and information on whether the subjects was able to treat him/herself or was asleep when the episode occurred.

A hypoglycaemic episode will be characterised as treatment emergent if the onset of the episode is on or after the first day the hyposafe H02 device switched to “*alarm on*”-mode and no later than the last day of the wearing the external device. Data on treatment emergent hypoglycaemic episodes are presented in terms of the number of subjects with at least one episode (N) and the number of episodes (E).

Hypoglycaemic episodes will be defined as nocturnal (i.e. during night-time) if they occur during sleep (as reported by the subject) and/or are registered by the hyposafe H02 night device.

Data from blood glucose measurement and clinical hypoglycaemia (according to subject’s experience) will be used by UNEEG™ medical to classify a hypoglycaemic alarm according to categorisation displayed in Table 2 (true and false, positive and negative hypoglycaemia alarms). As blood glucose values are lower than plasma values, a constant factor of 1.11 is used to convert concentration in whole blood to the equivalent concentration in plasma (25).

Sensitivity and positive predictive value will be calculated for daytime and night-time, separately.

Secondary performance endpoints

Insulin-induced hypoglycaemia is performed twice for each subject, with frequent assessments of plasma glucose levels. As the number of spontaneous hypoglycaemic episodes reported during the study may be relatively small, data from the insulin-induced hypoglycaemia will be added to calculate the overall **sensitivity and positive predictive value** of the hyposafe H02 (spontaneous and insulin-induced hypoglycaemia episodes) after 12 weeks of monitoring (from visit 5 to visit 10).

The sensitivity and positive predictive value will also be calculated based data from the insulin-induced hypoglycaemic episodes only.

The hypoglycaemic alarms will be classified according to categorisation displayed in Table 2 (true and false, positive and negative hypoglycaemia alarms), and presented as described for primary performance endpoint.

Table 2 Categorisation of hypoglycaemic episodes

Episodes categorised as			
PG > 3.9mmol/l	+ alarm	+/- clinical hypoglycaemia ^{a)}	False positive 
	- alarm	+/- clinical hypoglycaemia ^{a)}	True negative 
PG 2.0 – 3.9mmol/l	+ alarm	+/- clinical hypoglycaemia ^{a)}	True positive 
	- alarm	+ clinical hypoglycaemia ^{a)}	False negative 
		- clinical hypoglycaemia ^{a)}	True negative 
PG < 2.0mmol/l	+ alarm	+/- clinical hypoglycaemia ^{a)}	True positive 
	- alarm	+/- clinical hypoglycaemia ^{a)}	False negative 
PG not measured	+ alarm	+ clinical hypoglycaemia ^{a)}	True positive 
		- clinical hypoglycaemia ^{a)}	Not categorised 
	- alarm	+ clinical hypoglycaemia ^{a)}	Not categorised  False negative ^{b)} 

^{a)} According to subject (No strict definition is given)

^{b)} If hypoglycaemic episode was severe (i.e. requiring assistance from third person whether being help for carbohydrate ingestion, glucagon injection or contact to health care person), the episodes should be characterised as false negative

PG; plasma glucose

Data from **EEG quality test** at the visit 4 and visit 10 will be compared graphically.

The **impedance** is expected to be below 5 kOhm at all times. No trend in the measurements for each subject should be apparent over time, except perhaps a small decline in the beginning. Any change in impedance over time (from visit 5 to visit 10) will be summarised descriptively and presented by subject.

The **number of device complaints** will be tabulated and presented by device part.

Mean blood, plasma or interstitial **glucose level at the time of an alarm** will be summarised for insulin-induced hypoglycaemia and spontaneous hypoglycaemic episodes, separately.

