2.2 Endpoints

Primary performance endpoints

- Sensitivity: Proportion of spontaneous hypoglycaemic episodes detected by the hyposafe H02 compared to the total number of validated¹ spontaneous hypoglycaemic episodes after 12 weeks of monitoring (from visit 5 to visit 10)
- Positive predictive value: Proportion of validated¹ spontaneous hypoglycaemic episodes detected by the hyposafe H02 compared to the total number of alerts from the hyposafe H02 after 12 weeks of monitoring (from visit 5 to visit 10)

Secondary performance endpoints

- Overall sensitivity: Overall proportion of hypoglycaemic episodes detected by the hyposafe H02 compared to the total number of validated² hypoglycaemic episodes after 12 weeks of monitoring (from visit 5 to visit 10)
- Overall positive predictive value: Overall proportion of validated² hypoglycaemic episodes detected by the hyposafe H02 compared to the total number of alerts from the hyposafe H02 after 12 weeks of monitoring (from visit 5 to visit 10)
- Sensitivity: Proportion of insulin-induced hypoglycaemic episodes detected by the hyposafe H02 compared to the total number of insulin-induced hypoglycaemic episodes

¹ Validated by self-measured blood glucose (SMBG) or clinical hypoglycaemia according to subject's experience

² Validated by self-measured blood glucose (SMBG), plasma glucose (PG) or clinical hypoglycaemia according to subject's experience

- Positive predictive value: Proportion of insulin-induced hypoglycaemic episodes detected by the hyposafe H02 compared to the total number of alerts from the hyposafe H02
- Number of participants with a satisfactory EEG Quality test
- Change in impedance (from visit 5 to visit 10)
- Number of device complaints (from visit 4 to visit 10)
- Mean glucose level at the time of a hypoglycaemia alarm

Primary safety endpoint

- Number of AEs 17 weeks after implantation (from visit 3 to visit 12)

Secondary safety endpoint

- Number of adverse device effects (ADEs) 17 weeks after implantation (from visit 3 to visit 12)

Secondary usability endpoints

- Development in discomfort over time (visit 5 to visit 10)
- User satisfaction (visit 8)
- Mean number of hours of use per hyposafe H02 device (from visit 4 to visit 10)
- Response to hypoglycaemia alarm (from visit 5 to visit 10)
- Assessment of alarm fatigue (visit 12)

3 Study design - overview

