4.1 Definition of the overall subject population

Between 12 and 20 subjects with type 1 diabetes and impaired awareness of hypoglycaemia will be enrolled in the study to ensure a number of subjects completing the study of at least 12.

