7.5.3 Usability endpoints

All usability endpoints will be analysed using the FAS.

Development in discomfort over time

Data from questionnaires regarding discomfort related to the implanted device will be tabulated and presented by week and discomfort category and compared over time (visit 5 to visit 10).

Assessment of alarm fatigue

Data from questionnaire regarding alarm fatigue at visit 12 will be tabulated and presented by category of sensitivity and false alarm(s).

User satisfaction

Subject user satisfaction at visit 8 will be summarised based on the specific questionnaire.

Usage of external device

The mean number of hours the hyposafe H02 day or night device has been connected to the implant from visit 4 to visit 10 will be summarised. Summaries will be presented for daytime and night-time, separately.

Response to hypoglycaemia alarm

The number of preventive actions, i.e. the number of hypoglycaemia alarms where subject was able to take preventive action as instructed (acknowledge the alarm by key press, measure blood glucose, and in case of low blood glucose; ingest a carbohydrate rich meal) compared to the total number of hypoglycaemia alarms from visit 5 to visit 10 will be tabulated.

8 Ethics

The study will be conducted according to the Declaration of Helsinki (23) and approved by the local ethical committee before commencement. The use of the hyposafe H02 must be approved by the Danish Health and Medicines Agency before initiation. Only information relevant for the study will be collected. As UNEEG™ medical is a private data responsible the current private health research project will not been notified to the Danish Data Protection Agency. Data will be handled in accordance with the Act on Processing of Personal Data.

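### Section 2.2 and Table 2 imply different denominators for the primary sensitivity, and if Table 2 is used, some missed episodes are dropped while matching detected ones are kept.

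*Combined protocol and SAP*

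**What the plan says.** **Denominator.** Section 2.2 divides detected spontaneous episodes by all validated spontaneous episodes from visit 5 to visit 10. Footnote 1 defines validation: "Validated by self-measured blood glucose (SMBG) or clinical hypoglycaemia according to" the subject's experience. Either route is enough.

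**Source of episodes.** Section 7.5.1: "Spontaneous hypoglycaemic episodes are recorded by subjects in the log book throughout the study". The same log book holds the glucose value and the alarm.

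**Classification.** Under section 7.5.1 the sponsor classifies events by Table 2. When plasma glucose (PG) was not measured and the subject had symptoms, an alarm gives a true positive. Without an alarm the entry is *Not categorised*, and footnote b makes it a false negative only under a condition: "If hypoglycaemic episode was severe (i.e. requiring assistance from third person" and so on. For PG 2.0–3.9 mmol/l without symptoms, an alarm gives a true positive and no alarm gives a true negative. No formula links the Table 2 categories to the section 2.2 proportion.

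**Prompt to measure.** Section 7.5.3 describes the instructed response to an alarm: "acknowledge the alarm by key press, measure blood glucose, and in case of low blood glucose", eat. Section 4.1 states the population: "subjects with type 1 diabetes and impaired awareness of hypoglycaemia will be enrolled".

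**Time at risk.** A treatment-emergent episode is defined by calendar day, ending "no later than the last day of the wearing the external device". Wear is summarised as "The mean number of hours the hyposafe H02 day or night device has been connected to the implant".

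**Continuous glucose monitoring (CGM).** Section 3.1 has it mounted for two periods of about five days. It is in neither validation footnote of section 2.2 nor in Table 2. The only analysis that could draw on it is the interstitial "glucose level at the time of an alarm".

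**The concern.** A sensitivity estimate needs a reference that counts missed episodes as readily as detected ones. Two features work against that here.

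The first is a written rule. Two log-book entries that footnote 1 treats alike can be treated differently in Table 2 solely because one had an alarm. Where that happens, the detected episode stays in and the missed one goes out.

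The second is behaviour. An alarm tells the subject to measure. An un-alarmed episode gets no such prompt from the device, and these subjects are selected because they often fail to notice hypoglycaemia.

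This is the first primary performance endpoint. Section 1.2 says the study is to verify that the device works as intended before a larger study, and section 8.10 says the report will be used in further development and approval. As written, two analysts could obtain different primary results from the same log book.

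**Working it through.** The plan states no expected sensitivity and no episode count, so there is no figure of its own to reproduce.

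**Step 1. The two rules side by side.** The second row assumes that a self-measured value of 2.0–3.9 mmol/l validates an episode; footnote 1 gives no glucose limit.

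| Log-book entry | Section 2.2, footnote 1 | Table 2, alarm | Table 2, no alarm |
|---|---|---|---|
| Symptoms, no PG, not severe | validated | true positive | not categorised |
| PG 2.0–3.9, no symptoms | validated by measurement | true positive | true negative |
| PG 2.0–3.9, symptoms | validated | true positive | false negative |
| PG < 2.0 | validated | true positive | false negative |

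The last two rows are symmetric. The first two lose the un-alarmed episode from TP/(TP+FN) but keep the alarmed one.

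**Step 2. Effect of the rule.** Let s be the true sensitivity among validated episodes and u the share of un-alarmed validated episodes that Table 2 drops. Both are assumed, because the documents give neither.

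Reported sensitivity = s / [s + (1 − s)(1 − u)]

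| u | s = 0.60 | s = 0.90 |
|---|---|---|
| 0.10 | 0.60/0.96 = 62.5% | 0.90/0.99 = 91% |
| 0.25 | 0.60/0.90 = 67% | 0.90/0.975 = 92% |
| 0.50 | 0.60/0.80 = 75% | 0.90/0.95 = 95% |

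In counts: with 60 detected and 40 missed, dropping 10 of the 40 gives 60/90 = 67%. If the section 2.2 denominator governs, u = 0 and the shift is zero.

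**Step 3. Effect of recording.** Let r be the chance that a missed episode is logged and validated, relative to a detected one, on connected time. Reported sensitivity = s / [s + (1 − s)r]. For r = 0.75, 0.5 and 0.25 (assumed), s = 0.60 becomes 67%, 75% and 86%; s = 0.90 becomes 92%, 95% and 97%.

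**Step 4. Unworn time.** Suppose a share c = 0.8 of episodes falls in connected time (assumed), off-device episodes count as misses, s = 0.60 and r = 0.5. Then cs = 0.48.

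- Off-device episodes under-recorded at the same r: 0.48/(0.48 + 0.52 × 0.5) = 65%.
- Off-device episodes fully recorded: 0.48/(0.48 + 0.32 × 0.5 + 0.20) = 57%.

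These lie on either side of 60%, so the net direction over the whole window is not established.

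**Step 5. What CGM could show.** Two periods of 5 days within 84 days cover 10/84 = 12% of the window. Section 1.1.2 quotes prolonged nocturnal hypoglycaemia on 8.5% of nights, without a glucose limit. In 12 subjects, 12 × 10 × 0.085 = 10.2 such nights. If 5% to 20% of them fell below 2.0 mmol/l (assumed), 0.5 to 2.0 would be expected. The Poisson chance of seeing none is then exp(−0.51) = 60% down to exp(−2.04) = 13%, and clustering within subjects would raise it. Daytime episodes are not counted, so the yield is uncertain in both directions.

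**The case against.** The strongest reply is that section 2.2 defines the endpoint and Table 2 only sorts events. On that reading the un-alarmed symptomatic episode is already in the denominator and step 2 gives no bias. This stands as a possible reading. But section 7.5.1 places Table 2 inside the primary endpoint analysis and never says which rule yields the reported proportion.

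Second, the study is small and descriptive, with no success threshold (sections 7 and 7.1), and it adds two insulin-induced sessions per subject with frequent plasma glucose, reported alone and pooled. Those sessions do not depend on the log book, which is a real strength. They do not cover spontaneous episodes, and the pooled figure still contains the log-book episodes.

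Third, dependence on the alarm is only partial. Subjects can log symptomatic, self-tested or severe episodes without one. A reader might infer that no glucose testing is scheduled apart from alarms. The documents do not support that: the visit-by-visit instructions are not in the text available, so only the lack of a prompt from the device can be stated.

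Fourth, unworn time may belong to performance in everyday use, and section 7.5.1 ties the day-based definition to counts of subjects and episodes, not expressly to sensitivity. Both points are fair. Connected hours are reported by day and night, but mean hours cannot show whether a particular missed episode occurred off-device.

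**Conclusion.** The conflict between section 2.2 and Table 2 is plain on the text and should be resolved before analysis. If Table 2 supplies the denominator, sensitivity can only be raised: by 2.5 to 15 percentage points at a true 60%, and by about 1 to 5 at a true 90%, for assumed dropped shares of 10% to 50%. If section 2.2 supplies it, this component is zero. Separately, alarm-prompted recording tends to raise sensitivity on connected time by an amount the documents do not allow anyone to estimate.

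Three stronger readings are tempting but unsupported.

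- That the primary sensitivity will certainly be overstated. The Table 2 effect depends on which rule governs, and unworn time may act the other way.
- That only un-alarmed, unlogged episodes below 2.0 mmol/l are hidden misses. Table 2 also makes a symptomatic un-alarmed 2.0–3.9 episode a false negative.
- That CGM would settle the matter. Its coverage and expected yield are low, and section 1.2 itself notes user complaints of inaccuracy.

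**What to change.** 1. **Reconcile section 2.2 with Table 2.** State which episodes form the sensitivity denominator, and treat alarmed and un-alarmed episodes alike. Report the number of un-alarmed, symptomatic, non-severe episodes without PG. Give sensitivity with these as false negatives, and again with all symptoms-only episodes left out, alarmed or not. Also show the result with asymptomatic 2.0–3.9 mmol/l episodes handled the same way with and without an alarm. Cost: a short text change and a re-tabulation of log-book data.
2. **Label the primary figure** as sensitivity for subject-recorded, validated episodes. State that under-recording of misses raises it and that unworn time may lower it. Where time-stamped connection records exist, give the figure on connected time too. Cost: a sentence, plus time alignment; the plan commits only to mean hours.
3. **Optional: a descriptive table of the existing CGM periods,** outside the insulin-induced sessions, counting episodes as alarmed, logged only, or neither, separately for < 2.0 and 2.0–3.9 mmol/l. State that un-alarmed, unlogged 2.0–3.9 episodes cannot be classified without symptom data, that few or no episodes < 2.0 may be seen, and that a null result would not rule out under-recording. Cost: a written episode definition and an alarm-matching window.

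### The positive predictive value from insulin-induced hypoglycaemia does not measure the device's predictive value under any reading of the plan, and the overall value inherits part of the problem

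*Combined protocol and SAP*

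**What the plan says.** Section 2.2 lists as a secondary performance endpoint: "Positive predictive value: Proportion of insulin-induced hypoglycaemic episodes detected by the hyposafe H02 compared to the total number of alerts from the hyposafe H02". The primary and overall PPVs in the same list are tied to the 12 weeks from visit 5 to visit 10. This one has no window.

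Section 7.5.1 describes the source of the data: "Insulin-induced hypoglycaemia is performed twice for each subject, with frequent assessments of plasma glucose levels". Because few spontaneous episodes may be reported, it adds the induced data to form an overall sensitivity and PPV. It then states: "The sensitivity and positive predictive value will also be calculated based data from the insulin-induced hypoglycaemic episodes only".

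Alarms for these secondary endpoints are classified by Table 2. An alarm at plasma glucose (PG) above 3.9 mmol/l is a false positive. An alarm at any measured PG of 3.9 mmol/l or below is a true positive, with or without symptoms.

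The text does not say when an induced episode starts or ends, whether session time above 3.9 mmol/l belongs to it, how long that time lasts, or how repeat alarms are counted. No session without hypoglycaemia is described as a control.

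**The concern.** A PPV depends on how common the target condition is while the alarm is running. In an induced session the study itself makes the condition common, so the PPV reflects the procedure as well as the device. Sections 2.2 and 7.5.1 also leave the set of alerts open, so the same data could give very different figures depending on a choice made after they are seen.

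Section 1.2 says the study is to evaluate sensitivity and PPV and to verify that the device works before a larger study. Section 8.10 says the report will be used in further development and approval. An induced PPV would stand beside the primary PPV from everyday life without measuring the same thing. Because induced data are added to the overall PPV, the distortion reaches that endpoint too.

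**Working it through.** The plan states no PPV, target or precision, so there is no figure to reproduce. The check asks what the induced PPV would be under each reading, using as a benchmark an alarm that fires at random with respect to glucose.

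**Inputs from the documents.** Two induced sessions per subject (7.5.1). Between 12 and 20 subjects, with at least 12 completing (7.1), so 12 × 2 = 24 to 20 × 2 = 40 sessions. The 3.9 mmol/l cut-off (Table 2). Monitoring of 12 weeks (2.2).

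**Assumptions, because the documents give no figure.** The share *f* of session time at PG ≤ 3.9 mmol/l; one alert per session in reading 2; the rate of other alerts in everyday use.

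**Reading 1: only alarms inside episodes (PG ≤ 3.9 mmol/l).** No alarm can fall in the false-positive row, so PPV = TP/(TP + 0) = 100% for any device that alarms at least once.

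**Reading 2: all alarms in the session, classified by Table 2.** For the random alarm, TP ~ Binomial(*n*, *f*) and the expected PPV is *f*.

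| *f* (assumed) | Expected PPV | P(PPV ≥ 50%), n = 24 | P(≥ 22 of 24) | P(PPV ≥ 50%), n = 40 | P(≥ 36 of 40) |
|---|---|---|---|---|---|
| 0.5 | 50% | 58% | 0.002% | 56% | <0.001% |
| 0.6 | 60% | 89% | 0.07% | 93% | 0.003% |
| 0.7 | 70% | 99% | 1.2% | 99.8% | 0.3% |
| 0.8 | 80% | >99.9% | 11% | >99.9% | 7.6% |

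A random alarm would therefore very probably show a PPV of at least 50% once *f* is 0.6 or more, but would seldom reach about 90%. That changes if nearly the whole session is low: at *f* = 0.9 the chance of at least 22 of 24 is 56%. By the same rule, a random alarm in everyday life with an assumed 3-10% of time at or below 3.9 mmol/l would have a PPV of 3-10%.

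**Reading 2, with the Section 2.2 ratio taken literally.** The numerator counts episodes and the denominator counts alerts. With *k* alerts per session the ratio cannot exceed 1/*k*: 50%, 33% and 20% for *k* = 2, 3 and 5. Repeat alarms during one true episode lower the figure.

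**Reading 3: all alerts from visit 5 to visit 10.** With 12 subjects and all 24 induced episodes detected by one alert each, the maximum is 24/(24 + other alerts), where other alerts = 12 subjects × 12 weeks × weekly rate.

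| Other alerts per subject-week (assumed) | Other alerts | Maximum ratio |
|---|---|---|
| 0.25 | 36 | 24/60 = 40% |
| 1 | 144 | 24/168 = 14% |
| 7 | 1,008 | 24/1,032 = 2.3% |

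These ceilings apply even if every everyday alert is correct, because such alerts enter the denominator and never the numerator.

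**Overall PPV, illustration with assumed counts.** Take 50 everyday alerts of which 5% are true (2.5), plus 24 induced alerts all classed as true. The overall PPV is (2.5 + 24)/(50 + 24) = 26.5/74 = 36%, against 5% in everyday use.

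**The case against.** A reader might infer from 7.5.1 that the induced PPV is near 100% by construction and cannot separate a working alarm from a random one. The documents do not support that as a general statement. It follows only if alarms outside the low-glucose period are discarded, and no such rule is stated. The word *only* in 7.5.1 may simply separate the induced data from the pooled analysis just before it. The denominator in Section 2.2 is all alerts, Table 2 has a false-positive row, and frequent PG sampling allows that row to be filled. On the session reading a near-perfect result would usually stand out from chance over the assumed 50-80% range. On the 12-week reading the figure is low, not high. These points stand.

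It can also be said that the endpoint is secondary and descriptive, with no success threshold, that the primary PPV uses spontaneous episodes, and that glucose at the time of an alarm is summarised separately for induced and spontaneous episodes. This is correct and limits the consequences.

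It does not follow that defining the alert window would be enough. With the window fixed to the session, the PPV would still rest on a prevalence set by the procedure. With the window fixed to 12 weeks, everyday true alarms would still count against the device. A defined window makes the figure reproducible but does not make it a predictive value for use.

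**Conclusion.** The concern holds in this form: under every reading, the induced PPV fails to measure the device's predictive value. It is 100% for any device that alarms (episode data only), tied to the share of session time at or below 3.9 mmol/l (session alerts), or capped low (all visit 5 to visit 10 alerts). The 100% result and the reason for the low cap follow from the definitions. The sizes on the other two readings rest on assumed values: an expected 50-80% for a random alarm if 50-80% of session time is low, and a ceiling of 40% to 2.3% for 0.25 to 7 other alerts per subject-week. The overall PPV is shifted by the same artificial prevalence, by an amount that depends on the mix of induced and everyday alerts.

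The induced sensitivity is not affected by this point, and neither is the primary PPV. The change should be made, but its weight is that of a secondary, descriptive endpoint.

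**What to change.** In Sections 2.2 and 7.5.1:

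- Keep the sensitivity from induced hypoglycaemia.
- Replace the induced PPV with two measures from the plasma glucose already sampled: false alarms at PG > 3.9 mmol/l per hour of session time above 3.9 mmol/l, and the number of sessions with an alarm before PG first reached 3.9 mmol/l.
- State that any PPV interpreted as device performance is based on everyday (spontaneous) alarms only.
- If the induced or overall PPV is retained, restrict its denominator to a stated alert window that includes session time above 3.9 mmol/l, state how repeat alarms count, show induced and everyday counts separately, and label the figure as not transferable to everyday use.

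The cost is a few sentences and one small table, with no added subjects or procedures. One favourable-looking secondary figure is dropped or demoted, and an overall PPV without the induced alarms rests on fewer alarms. Where session time above 3.9 mmol/l is short, the false-alarm rate will be imprecise, so the hours observed should be shown beside it.
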